18.6 Specification of the Secondary Analyses

A Wilcoxon test will be used to calculate the P(X<Y) and the p-value for the clinical composite score endpoint. Multivariate rank-ordered data will be analyzed according to the worst-rank approach of Lachin¹²³. A mixed model repeated measures (MMRM) analysis will be used to compare differences in the slope of peak VO2 and 6MW distance across the two treatment groups¹²⁴. Contrast estimates of differences in slopes of treatment by time (along with confidence intervals) will be used to estimate the treatment effect. The validity of this model in terms of meeting modeling assumptions will be assessed via standard modeling diagnostics and goodness-of-fit measures. Based on the MMRM framework, missing peak VO2 and 6MW distance data will not be imputed. Sensitivity analyses will be conducted using an inverse probability weighted method to account for missing data¹²⁵.

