6. BASIC STUDY DESIGN

Study Design: Randomized (1:1), double-blind, placebo controlled treatment study

Intervention: PDE-5 inhibition with sildenafil (20 mg tid for 12 weeks followed by 60 mg tid for 12 weeks) or placebo for 24 weeks

Study population: Approximately 215 patients with a clinical diagnosis of HF and normal EF (\geq 50%) enrolled over a planned 3.25 year enrollment period.

Primary outcome: The primary endpoint will be exercise capacity as assessed by the change in peak VO_2 at 24 weeks of double blinded therapy compared to the baseline peak VO_2 .

Secondary outcomes:

1. Change in a composite score reflective of clinical status after 24 weeks of double-blinded treatment with PDE-5 inhibitor or placebo.

2. Change in submaximal exercise capacity at 12 and 24 weeks as assessed by 6 minute walk test

3. Change in peak VO₂ at 12 weeks

Additional tertiary endpoints will explore potential mechanisms whereby PDE-5 inhibition may exert benefit on exercise capacity and clinical status.

- 1. Change in exercise time at 12 and 24 weeks
- 2. Change in ventilatory anaerobic threshold (VAT) at 12 and 24 weeks
- 3. Change in MLWHFQ at 12 and 24 weeks
- 4. Change in LV mass and serological markers of extracellular matrix metabolism at 24 weeks

5. Change in LV diastolic function (LV relaxation, diastolic elastance and filling pressure by Doppler) at 24 weeks

6. Change in peripheral vascular function (effective arterial elastance (Ea), systemic vascular resistance (SVR) and aortic thickness and distensibility) at 24 weeks

7. Change in pulmonary hemodynamics (Doppler estimated pulmonary artery systolic pressure (PASP) at 24 weeks

8. Change in neuroendocrine function (Cyclic guanosine monophosphate (cGMP), N-terminal pro-brain natriuretic peptide (NT-proBNP) and aldosterone) at 24 weeks

9. Change in renal function (creatinine, estimated glomerular filtration rate (GFR), cystatin C and diuretic dose) at 24 weeks

Duration:

Consent, Screening studies (up to 2 weeks) Baseline studies and Randomization (up to 2 weeks) Treatment phase (24 weeks)

Frequency of study related visits:

- 1. Consent
- 2. Screening labs and cardiopulmonary exercise test (if needed)
- 3. Baseline studies (in patients meeting eligibility requirements)
- 4. Randomization and initial dosing (wk 0, 20 mg tid)
- 5. Week 3 study visit and safety labs (+/- 7 days)
- 6. 12 week visit, studies and dose escalation (60 mg tid) (+/- 7 days)
- 7. 24 week visit and studies (+/- 7 days)

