14.2 Secondary and Tertiary Outcomes

14.2.1 Composite Clinical Score

A composite clinical score in RELAX will be based on a ranking of all participants. All participants will be ranked sequentially with ranking stratified in one of three tiers based on:

1) Death (lowest tier)

The ranking within this tier is based on time to death from randomization date. The person with the shortest time from randomization to death is given the lowest rank within the tier.

2) Hospitalizations due to cardiovascular (CV) or renal causes (middle tier)

For patients alive, the ranking within this tier is based on time to hospitalization from randomization date. The person with the first cardiovascular or renal cause hospitalization will be given the lowest rank within the tier. Cardiovascular causes defined as initial primary cause for hospitalization as HF, acute coronary syndrome, cerebrovascular accident, peripheral vascular disease, arrhythmia or syncope. Renal causes defined as initial primary cause for hospitalization, renal failure or hyperkalemia.

3) Change in MLWHFQ from baseline (highest tier)

For patients without an event meeting the first two criteria, the person with the least favorable change in MLWHFQ is given the lowest rank within this tier. Patients with an equal change in the MLWHFQ will receive an equal ranking.

The use of three tiers within the ranking reflects the greater adverse impact of death or CV hospitalization on clinical status without an arbitrary assignment as to the relative value of these events in relation to changes in quality of life.

14.2.2 Minnesota Living with Heart Failure Questionnaire:

The MLWHFQ is a self-administered, disease-specific measure of health related quality of life (QOL) that assesses patients' perceptions of the influence of HF on physical, socioeconomic and psychological aspects of life⁹⁶⁻⁹⁸. Patients respond to 21 items using a six-point response scale (0-5). The total summary score can range from 0-105 with a lower score reflecting better HF related QOL. Two subscale scores reflect physical (8 items) and emotional (5 items) impairment. This instrument has been extensively validated and widely used to assess treatment effect on clinical status in multiple trials of therapeutic interventions in HF.

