18.1.2 Secondary Endpoints: Composite clinical score

A composite clinical score in RELAX will be based on a ranking of all participants. All participants will be ranked sequentially with ranking stratified in one of three tiers based on:

1) Death (lowest tier)

The ranking within this tier is based on time to death from randomization date. The person with the shortest time from randomization to death is given the lowest rank within the tier.

2) Hospitalizations due to cardiovascular (CV) or renal causes (middle tier)

For patients alive, the ranking within this tier is based on time to hospitalization from randomization date. The person with the first cardiovascular or renal cause hospitalization will be given the lowest rank within the tier. Cardiovascular causes defined as initial primary cause for hospitalization as HF, acute coronary syndrome, cerebrovascular accident, peripheral vascular disease, arrhythmia or syncope. Renal causes defined as initial primary cause for hospitalization, renal failure or hyperkalemia.

3) Change in MLWHFQ from baseline (highest tier)

For patients without an event meeting the first two criteria, the person with the least favorable change in MLWHFQ is given the lowest rank within this tier. Patients with an equal change in the MLWHFQ will receive an equal ranking.

The use of three tiers within the ranking reflects the greater adverse impact of death or CV hospitalization on clinical status without an arbitrary assignment as to the relative value of these events in relation to changes in quality of life.

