18.2 Analysis Policies

A statistical analysis plan will be completed before the data are analyzed in an unblinded fashion. Due to clinical interest in departures from both sides of the null hypothesis, all test statistics will be twosided. The trial results will be reported according to guidelines specified in the CONSORT statement^{121,122}. A flow diagram describing screening, recruitment, randomization, dropout, and vital status will be included in the primary manuscript. Adverse events and efficacy data will be presented by the two treatment groups. Adherence, dropout, and lost-to-follow-up will be carefully examined across the two treatment groups. Analyses of safety will be based on data from all randomized patients who received at least 1 dose of study drug. All primary analyses will be based on intent-to-treat (ITT) principles using all randomized participants.

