18.2.1 Controlling Type-I Error

The primary endpoint of change in peak VO2 from baseline to 24 weeks will be evaluated at the twosided 0.05 level. A conservative approach will be taken with the multiple analyses on key clinical subgroups. For subgroup analyses, a significance level of 0.001 will be required for statistical significance. Thus, subgroup analyses will be considered exploratory unless the p-value from an interaction test is smaller than 0.001.

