18.5 Specification of the Primary Analyses

A general linear model with the change in peak VO2 measured at 24 weeks compared to the baseline peak VO_2 as the response variable and predictor variables including a treatment indicator and the baseline measure of peak VO2 will be used in the primary analysis. The treatment effect will be determined by the point estimate and 95% confidence interval for the treatment indicator.

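### The composite clinical score ranks event-free patients on raw MLWHFQ change with no adjustment for baseline MLWHFQ: a valid analysis, but one that gives up precision cheaply recovered

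*Protocol*

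**What the plan says.** Sections 14.2.1 and 18.1.2 define the composite in identical terms. Deaths rank lowest, ordered by time to death. Cardiovascular or renal hospitalizations come next, ordered by time to hospitalization. Everyone else is ordered by change in MLWHFQ: "For patients without an event meeting the first two criteria, the person with the least favorable change in MLWHFQ is given the lowest rank". Section 14.2.2 describes the scale: "The total summary score can range from 0-105 with a lower score reflecting better HF related QOL".

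The comparison of arms is fixed in Section 18.6: "A Wilcoxon test will be used to calculate the P(X<Y) and the p-value for the clinical composite score endpoint". No covariate or stratification factor is attached to it. Section 18.2 adds that "all test statistics will be twosided".

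The primary analysis in Section 18.5 is handled differently. The response is also a change from baseline, but the model has "predictor variables including a treatment indicator and the baseline measure of peak VO2".

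Baseline MLWHFQ is a scheduled baseline evaluation (Section 12.1 and Appendix 1). Section 18.4 promises an adjusted analysis if baseline characteristics differ significantly between arms. It names neither MLWHFQ nor the composite.

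**The concern.** When a follow-up score correlates imperfectly with its baseline, raw change is negatively correlated with that baseline. Subtracting the whole baseline over-corrects, which adds variance and lets a chance baseline difference between arms enter the ranks. The protocol avoids this for peak VO2 but not for the composite.

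The scale is bounded at 0 and NYHA class II to IV patients are eligible, so starting scores should be widely spread. A patient who goes from 8 to 0 reaches the best possible score with a change of 8. That patient ranks below one who goes from 80 to 70, a change of 10.

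The stake is the precision of the first-listed secondary endpoint, in a trial that Section 18.4 itself describes as small enough for baseline imbalance to be a possibility. The ranking variable and the test are both named, so this is a stated choice and not a detail left open.

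**Working it through.** **Inputs from the protocol.** 190 analysed patients and P(X<Y) = 0.65 with 80% power (Section 18.1.2); 1:1 allocation (Section 6); two-sided tests (Section 18.2). Alpha 0.05 is stated only for the primary endpoint and is assumed here for the composite.

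**Inputs the protocol does not give.** MLWHFQ SD, baseline-to-week-24 correlation (rho), benefit in points and expected tier shares. All are assumed below.

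**Step 1: the plan's own figure.** Noether's formula for the Wilcoxon test with 1:1 allocation is power = Phi(sqrt(12 x N x 0.25) x |P - 0.5| - 1.96).
- N = 190, P = 0.65: sqrt(570) x 0.15 - 1.96 = 3.58 - 1.96 = 1.62, so power is 94.8%. The stated 80% is not reproduced.
- 80% power at P = 0.65 needs (1.96 + 0.842)^2 / (3 x 0.15^2), about 116 patients. With 190 patients, 80% power is reached at P = 0.617.
- The stated figure is conservative, so the unadjusted test does not fall short of its plan.

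**Step 2: raw against adjusted change, ignoring the event tiers.** With equal SD s at both visits, raw change has variance 2s²(1 - rho) and the residual on baseline has s²(1 - rho²). The ratio is (1 + rho)/2. Patients saved out of 190 are 190 x (1 - rho)/2. The raw analysis would need 190 x 2/(1 + rho) to match.

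| rho | variance ratio | saved of 190 | raw N needed to match |
|---|---|---|---|
| 0.5 | 0.75 | 48 | 253 (+63) |
| 0.6 | 0.80 | 38 | 238 (+48) |
| 0.7 | 0.85 | 29 | 224 (+34) |
| 0.8 | 0.90 | 19 | 211 (+21) |

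Over rho from 0.3 to 0.9 the saving runs from 67 down to 10 of 190.

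**Step 3: simulation of the tiered score.** Assumed: N = 190, SD 22, mean baseline 45, 5-point background improvement, 8-point treatment benefit, scores rounded and clipped to 0-105, 3,000 runs per scenario. Power for raw-change ranking against residual ranking in the top tier:
- Events 20% in both arms, rho 0.6: 38% against 47%. Raw ranking with 240 patients gives about 47% to 48%.
- Events 10% to 30%, rho 0.5 to 0.7: gain of about 5 to 13 points.
- Events 20%, rho 0.8: 65% against 72%.
- Treatment also lowers events from 25% to 17%, rho 0.6: 75% against 81%. With 25% against 15%: 83% against 88%.
- Effect raised until P(X<Y) = 0.65 (rho 0.6, events 20%): 95.6% against 98.5%.
- No effect: type I error 5.0% against 5.5%.

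A second simulation held the effect at 0.42 SDs of the raw change. With events 25% against 17%, its gains were 5.7 points at rho 0.5 (79.3% to 85.0%), 3.0 at 0.7 and 1.8 at 0.8. The gain is therefore smaller when the correlation is high and events also carry the effect.

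**Step 4: a covariate-adjusted rank test instead.** Regressing the composite rank on the baseline rank gave 42% in the rho 0.6, 20% events scenario, between 38% (raw) and 47% (residual). In the second simulation at rho 0.5 its saving fell from about 41 patients with no events to 22 at 13% events, 11 at 25% and 5 at 40%. The two remedies are not interchangeable.

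**The case against.** The strongest reply is that nothing here is wrong. Under randomization the unadjusted Wilcoxon test holds its type I error and estimates P(X<Y), the quantity on which Section 18.1.2 bases its power. At the planned value of 0.65 that power is about 95%, leaving little room for improvement. The 38% against 47% contrast arises at P(X<Y) of about 0.57, well below the planning effect. Covariate adjustment could also be set in the analysis plan that Section 18.2 promises. All of this stands, and it fixes the rank of the point: an improvement, not a defect.

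Ranking by change is also a choice of estimand. Residual ranks depend on a fitted line and can place a 10-point improver below an 8-point improver. That is a real cost in directness.

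Three stronger readings are tempting and not supported:
- A reader might infer that baseline MLWHFQ is ignored. It is subtracted in the change score; what is missing is adjustment for it.
- A reader might infer a fixed loss of about 50 patients. That figure needs a correlation of about 0.6 (as extra patients for the raw analysis) or 0.5 (as patients saved), and the protocol gives neither.
- A reader might infer that planned power is missed. Step 1 shows the opposite.

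The conditional adjustment in Section 18.4 does not answer the point. It depends on a significant imbalance being seen, does not name this endpoint, and would forgo the precision gain whenever no imbalance is significant.

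**Conclusion.** The point holds as an inexpensive efficiency improvement to a stated method for a secondary endpoint. The planned analysis is valid. Residual ranking had higher power than raw ranking in every non-null scenario examined, with type I error near 5%.

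The size is conditional. Under N = 190, SD 22, an 8-point benefit, correlation 0.5 to 0.8 and events of 10% to 30%, the gain is about 5 to 13 percentage points. If treatment also lowers events it is about 6 to 7 points at correlations of 0.5 to 0.6, and less at higher correlations. Near P(X<Y) = 0.65 it is about 3 to 5 points. No single patient count should be attached to it, because the protocol supplies none of the inputs that determine one.

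**What to change.** Keep the three tiers. Before unblinding, state in Sections 14.2.1, 18.1.2 and 18.6 that event-free patients are ranked on the residual of week-24 MLWHFQ on baseline MLWHFQ, from one regression pooled over both arms. The Wilcoxon test is then applied to the resulting ranks, and the raw-change ranking is reported as supportive.

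If the raw-change definition is to be kept, replace the unadjusted test with a rank test that has baseline MLWHFQ as a covariate. This is not equivalent. Its gain is smaller, about 0 to 8 points under the assumed ranges, and shrinks as events rise.

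The cost is about one sentence in each section and a few lines of code, with no new data. The downside is that a residual rank is slightly less direct to explain than a raw change, which the supportive analysis helps to cover.

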2. EXECUTIVE SUMMARY

Study Design: This is a double-blind, placebo controlled study testing the hypothesis that chronic PDE-5 inhibition (Sildenafil) improves exercise capacity and clinical status in patients with heart failure (HF) and normal ejection fraction (diastolic HF, DHF). The study also measures the effect of this therapy on key pathophysiological parameters which are postulated to impact clinical status and exercise performance in DHF. Approximately 215 patients with DHF will be studied.

Intervention: PDE-5 inhibition (Sildenafil) vs Placebo (20 mg tid for 12 weeks followed by 60 mg tid for 12 weeks).

Enrollment period: Patients will be enrolled over a 3.25 year period.

Rationale for this study is provided by proven benefits of PDE-5 inhibition in patients with pulmonary hypertension, emerging evidence of benefit in HF with systolic dysfunction in pre-clinical and early clinical studies, seminal studies in animal models of pressure overload suggesting unique activation of cardiac PDE-5 in pressure overload hypertrophy and animal studies suggesting that PDE-5 up-regulation mediates hypo-responsiveness to natriuretic peptides and contributes to sodium retention in HF. In aggregate, these studies suggest PDE-5 inhibition may provide beneficial effects on the heart, peripheral vasculature, pulmonary vasculature, kidney and neuroendocrine function. Such multi-system effects suggest the potential for PDE-5 inhibition to ameliorate several key pathophysiological perturbations and thus, improve exercise capacity and clinical status in DHF.

Primary Endpoint: The primary endpoint will be the change in exercise capacity as assessed by peak VO_2 after 24 weeks of double-blinded treatment with PDE-5 inhibitor or placebo.

Secondary Endpoints:

1. Change in a composite score reflective of clinical status after 24 weeks of therapy.

- 2. Change in submaximal exercise capacity at 12 and 24 weeks as assessed by 6 minute walk test
- 3. Change in peak VO₂ after 12 weeks of therapy

Tertiary Endpoints

1. Change in exercise time at 12 and 24 weeks

2. Change in ventilatory anaerobic threshold (VAT) at 12 and 24 weeks

3. Change in MLWHFQ at 12 and 24 weeks

4. Change in LV mass (assessed by cardiac MRI) and serological markers of extracellular matrix metabolism at 24 weeks

5. Change in LV diastolic function (LV relaxation, diastolic elastance and filling pressure by Doppler) at 24 weeks

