6. Change in peripheral vascular function (effective arterial elastance (Ea), systemic vascular resistance (SVR) and aortic thickness and distensibility) at 24 weeks

7. Change in pulmonary hemodynamics (Doppler estimated pulmonary artery systolic pressure (PASP)) at 24 weeks

8. Change in neuroendocrine function (Cyclic guanosine monophosphate (cGMP), N-terminal pro-brain natriuretic peptide (NT-proBNP) and aldosterone) at 24 weeks

9. Change in renal function (creatinine, estimated glomerular filtration rate (GFR), cystatin C and diuretic dose) at 24 weeks

Pre-specified subgroup analysis will include comparison of the effect of therapy in patients with:

- 1. LV mass index above and below the median at entry into the study.
- 2. Estimated PASP above and below the median at entry into the study
- 3. Dose of sildenafil achieved
- 4. Presence of atrial fibrillation
- 5. Differences in background therapy

Primary Hypothesis: As compared to placebo, chronic PDE-5 inhibition will result in greater improvement in exercise performance as measured by peak VO_2 in DHF after 24 weeks of double blinded therapy.

Secondary Hypotheses:

- 1. As compared to placebo, chronic PDE-5 inhibition will result in greater improvement in clinical status at 24 weeks.
- 2. As compared to placebo, chronic PDE-5 inhibition will result in greater improvement in submaximal exercise capacity as assessed by 6 minute walk distance at 12 and 24 weeks.
- 3. As compared to placebo, chronic PDE-5 inhibition will result in improved exercise performance as measured by peak VO₂ after 12 weeks.
- 4. As compared to placebo, chronic PDE-5 inhibition will result in greater improvement in other measures of exercise capacity (exercise time and VAT) at 12 and 24 weeks.
- 5. As compared to placebo, chronic PDE-5 inhibition will result in greater improvement in quality of life as assessed by the MLWHFQ score at 12 weeks and 24 weeks.
- 6. As compared to placebo, chronic PDE-5 inhibition will result in greater reduction in LV mass, serological markers of LV fibrosis, diastolic dysfunction, peripheral vascular dysfunction, pulmonary vascular dysfunction, humoral activation and renal dysfunction at 24 weeks.
- 7. Increasing the dose of sildenafil from 20 mg tid to 60 mg tid will result in further improvement in exercise performance as measured by peak VO_2 and 6 minute walk distance.

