9. TREATMENT INTERVENTIONS

9.1 Intervention

The therapeutic intervention is double blinded therapy with placebo or the PDE-5 inhibitor sildenafil (as Revatio[®]). Study drug therapy will be given for 24 weeks starting with 20 mg by mouth three times a day (tid) for 12 weeks. If that dose is well tolerated, the dose will be increased to 60 mg tid at week 12 for the remaining 12 weeks of the study. Patients unable to tolerate the 60 mg tid will be maintained on the 20 mg tid dose. The active and placebo study medication will appear identical to preserve the double blind design of the study. If patients develop side effects thought potentially related to study drug (including but not limited to headache, flushing, dizziness, orthostatic lightheadedness, dyspepsia, nasal congestion, diarrhea, rash, visual disturbance), the dose will be adjusted to the previously tolerated dose. As recommended for patients with HF, patients will be encouraged to weigh daily and record weights. If patients have experienced enhanced responsiveness to their diuretic dosage (decreased weight *and* symptoms of over-diuresis such as lightheadedness), consideration can be given to reducing the diuretic dose rather than the study drug.

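### Section 18.6 estimates the treatment effect on peak VO2 and 6-minute walk by a difference in slopes, which does not estimate the stated 12-week secondary endpoints

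*Protocol*

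**What the plan says.** Section 2 lists the secondary endpoints by visit: "Change in submaximal exercise capacity at 12 and 24 weeks as assessed by 6 minute walk test" and "Change in peak VO₂ after 12 weeks of therapy". Section 6 repeats them, and secondary hypotheses 2 and 3 are framed at the same visits.

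Section 18.6 gives the only analysis specified for these endpoints. The mixed model "will be used to compare differences in the slope of peak VO2 and 6MW distance across the two treatment groups", and the estimator is then fixed: "Contrast estimates of differences in slopes of treatment by time (along with confidence intervals) will be used to estimate the treatment effect". No contrast at week 12 or week 24 is named. Missing values are not imputed, and an inverse-probability-weighted sensitivity analysis is planned.

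Three other places bear on the point:

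- Section 9.1: if the first dose is well tolerated, "the dose will be increased to 60 mg tid at week 12".
- Section 2, secondary hypothesis 7: "Increasing the dose of sildenafil from 20 mg tid to 60 mg tid will result in further improvement in exercise performance". Section 9.4, by contrast, acknowledges that going above the first dose may add nothing.
- Section 18.5: peak VO2 at 24 weeks, the primary endpoint, has its own general linear model on the 24-week change, adjusted for baseline.

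**The concern.** A slope difference is one number per endpoint. It can stand for effects at two visits only if the treatment difference grows in a straight line from baseline through week 12 to week 24. The design gives no ground for that. The dose steps up at week 12, hypothesis 7 expects a gain from the step, and section 9.4 allows that the effect may already be complete before it. Separate 12- and 24-week endpoints can tell these profiles apart, and the slope cannot.

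At stake are the 12-week comparisons with placebo for peak VO2 and 6MW. Under the stated estimator a real early effect could be understated, or an absent one implied.

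**Working it through.** **The plan's own figure.** Section 18.1.3 gives 90% power for a 33 m difference in 6MW change, with SD 70 m and 190 analysed patients (95 per arm). Standard error = 70 × √(2/95) = 10.16 m; 33/10.16 = 3.25; power = Φ(3.25 − 1.96) = 0.90. The figure reproduces. It is a two-group comparison of changes at one visit, so it matches a visit contrast. The protocol gives no power figure for a slope.

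**Inputs.** Visits at 0, 12 and 24 weeks (section 13.1); effect sizes 1.2 ml/kg/min (section 18.1.1) and 33 m (section 18.1.3); 10% missing for 6MW (section 18.1.3). The trajectories, the correlations and the split of missing data are assumptions, because the protocol gives none.

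**Weights.** With complete data, equal spacing and compound symmetry, the generalised least squares slope puts weight (t − 12)/Σ(t − 12)² on each visit, that is (−12, 0, +12)/288. Multiplied by 24 weeks the weights are (−1, 0, +1). With no baseline difference between randomised arms:

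- slope × 24 = the true week-24 difference;
- slope × 12 = half the true week-24 difference, whatever happened at week 12.

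| Endpoint | True effect, week 12 / week 24 | Slope × 12 | Slope × 24 |
|---|---|---|---|
| Peak VO2 (ml/kg/min) | 1.2 / 1.2 | 0.60 | 1.20 |
| Peak VO2 (ml/kg/min) | 0.6 / 1.2 | 0.60 | 1.20 |
| Peak VO2 (ml/kg/min) | 0 / 1.2 | 0.60 | 1.20 |
| 6MW (m) | 33 / 33 | 16.5 | 33.0 |
| 6MW (m) | 0 / 33 | 16.5 | 33.0 |

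Only the linear profile (0.6 / 1.2) is right at both visits. Reading the fitted line at week 12 instead of multiplying the slope does not help. With separate baselines the fitted difference there is the mean of the three visit differences: (0 + 33 + 33)/3 = 22 m when the truth is 33, and (0 + 0 + 33)/3 = 11 m when the truth is 0.

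**Week 24 with missing data.** The model has separate baselines by arm and compound symmetry. At the protocol's 10% missing for 6MW, half of those patients having a week-12 value, and correlation 0.6, slope × 24 is 33.5 m for a true 33/33 and 32.5 m for a true 0/33. The error is 0.5/33, about 1.6%; correlations up to 0.85 give almost the same. Unequal variances matter more: with assumed SD ratios 1 : 1.15 : 1.3, correlation 0.7 and complete data, the same two cases give 35.9 m and 30.2 m, an error of about 8.6% (2.85/33).

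**With categorical visits.** Each treatment-by-visit contrast targets the true difference at its own visit, whatever the trajectory.

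**The case against.** The best defence is that the wording is loose, not wrong. A model called MMRM usually treats visit as categorical, section 18.6 never says that time is linear, and treatment-by-time contrasts could be visit contrasts. Section 18.2 promises an analysis plan before unblinded analysis, and section 18.6 promises checks of model fit. Section 9.4 also plans an exploratory comparison of exercise capacity on the two doses. Finally, nothing says that anyone will multiply the slope by 12 and report it as the 12-week effect.

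Some of this stands. The intent may well have been visit contrasts, and the halved figures are what the slope implies, not a result the protocol promises to report. But section 18.6 names slopes twice, makes their difference the estimator, and names no visit contrast. This is a stated estimator that misses the endpoint, not a detail left open. If nobody converts the slope to week 12, the section contains no 12-week estimate at all. The fit checks carry no stated action if linearity fails. The section 9.4 comparison is confined to sildenafil patients, so it does not replace a contrast with placebo.

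A reader might also infer that the 24-week results are compromised. The documents do not support that. Peak VO2 at 24 weeks is analysed under section 18.5 without any slope. For 6MW, slope × 24 is exact in the complete, balanced, compound-symmetric case and close to it at the protocol's own missing rate.

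**Conclusion.** The concern holds for the 12-week endpoints. Read literally, section 18.6 cannot estimate the 12-week change in peak VO2 or 6MW unless the treatment difference is linear in time. With a week-24 effect of 1.2 ml/kg/min or 33 m, the implied week-12 effect is 0.60 or 16.5 m whether the true week-12 effect is the full amount or nothing. That result needs no missing-data assumption; it rests on linear time and, for the exact zero weight, on complete equally spaced data with compound symmetry.

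The 24-week 6MW problem is minor: no error in that same case, and about 1.6% at 10% missing under the assumptions shown, though more if variances differ across visits. The primary analysis and the sample size are untouched. This should be fixed before unblinded analysis, as a matter of secondary endpoints only.

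**What to change.** In section 18.6, replace the slope contrast with an MMRM of the week-12 and week-24 responses: visit as a categorical factor, treatment-by-visit interaction, baseline value as covariate and unstructured covariance. State that the treatment contrasts reported are 6MW at week 12, 6MW at week 24, and peak VO2 at week 12. Keep the section 18.5 model as the primary analysis of peak VO2 at week 24, and say so, so that the repeated-measures model does not yield a competing primary result.

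The cost is about two sentences and a few more model parameters. Data, visits, software and sample size do not change, and the 6MW power statement in section 18.1.3 already describes a single-visit comparison. Patients with no post-baseline value contribute nothing to this model; the weighted sensitivity analysis already planned can stay to address missing data.
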